3.1.1.3. Fever

Temperatures will be taken orally. Temperature will be collected in the reactogenicity e-diary daily for 7 days or longer following vaccination (where Day 1 is the day of vaccination). It will also be collected at any time during the reactogenicity e-diary data collection period when fever is suspected. Fever is defined as an oral temperature of ≥38.0°C (≥100.4°F). The highest temperature for each day will be recorded in the e-diary.

Temperature will be measured and recorded to 1 decimal place. Temperatures recorded in degrees Fahrenheit will be programmatically converted to degrees Celsius for reporting. Temperatures <35.0°C (<95°F) and >42.0°C (>107.6°F) will be excluded from the analysis. Fever will be grouped into ranges for the analysis according to Table 5.

Table 5. Scale for Fever

| ≥38.0-38.4°C (100.4-101.1°F) |
|------------------------------|
| >38.4-38.9°C (101.2-102.0°F) |
| >38.9-40.0°C (102.1-104.0°F) |
| >40.0°C (>104.0°F) |

3.1.1.4. Use of Antipyretic/Pain Medication

The use of antipyretic/pain medication is also recorded in the e-diary from Day 1 through Day 7, where Day 1 is the day of vaccination. For the use of antipyretic/pain medication from Day 1 through Day 7, the following endpoints and variables will be derived:

- Presence (yes or no) of use of antipyretic/pain medication on each day (Day 1 through Day 7)
- Presence (yes or no) of use of antipyretic/pain medication on any day (Day 1 through Day 7)
- Duration (first to last day reported) of use of antipyretic/pain medication
- Onset day of use of antipyretic/pain medication

The use of antipyretic/pain medication will be summarized and included in the systemic event summary tables but will not be considered a systemic event.

3.1.1.5. Adverse Events

AEs are collected from the completion of informed consent through 4 weeks (Visit 2) after study vaccination. SAEs are collected from the completion of informed consent through 6 months after study vaccination (Visit 3). Additionally, any AEs occurring up to 48 hours after a blood draw must be recorded. AEs/SAEs will be categorized according to MedDRA terms.

The safety primary endpoints "AEs from vaccination through 4 weeks after vaccination" and "SAEs from vaccination through 6 months after vaccination" will be summarized, by SOC and PT, at the participant level for each vaccine group within each cohort.

These safety primary endpoints will be supported by summaries and/or listings of related AEs, severe AEs, immediate AEs (within the first 30 minutes after the study vaccination), and AESIs (defined in Section 8.4.8 of the protocol). Partially missing AE start dates will be imputed following the Pfizer data standard rules as described in Section 5.3.

3.1.2. Immunogenicity Endpoints

In Cohort 2 participants who receive the study intervention (BNT162b2 or QIV administered concomitantly with BNT162b2 [Omi XBB.1.5]):

- HAI titers (from HAI based on CCI derived virus) for each matched seasonal strain recommended by WHO at 4 weeks after study vaccination.
- SARS-CoV-2 (Omi XBB.1.5)—neutralizing titers at 4 weeks after study vaccination.

3.2. Secondary Endpoint(s)

In Cohort 3 participants who receive the study intervention (BNT162b2, QIV alone, or alone):

HAI titers (from HAI based on CCI derived virus) for each matched seasonal strain recommended by WHO at 4 weeks after study vaccination.

In Cohort 3 participants who receive the study intervention (COM BNT162b2 or BNT162b2 [Omi XBB.1.5] alone):

SARS-CoV-2 (Omi XBB.1.5)—neutralizing titers at 4 weeks after study vaccination.

In Cohort 2 participants who receive the study intervention (CCI BNT162b2 or QIV administered concomitantly with BNT162b2 [Omi XBB.1.5]):

HAI titers (from HAI based on CCI derived virus) for each matched seasonal strain recommended by WHO at 4 weeks after study vaccination.

3.3. Other Safety Endpoint(s)

All safety endpoints are described in Section 3.1.1.

3.5. Baseline Variables

3.5.1. Demographics and Medical History

The demographic variables are age, sex (male or female), race (Black/African American, American Indian or Alaska Native, Asian, Native Hawaiian or other Pacific Islander, White, and not reported), and ethnicity (Hispanic/Latino, non-Hispanic/non-Latino, and not reported).

For reporting of race, where more than 1 category is selected for race, the participant would be counted under the category "multiracial" for analysis.

Medical history will be categorized according to MedDRA.

3.5.2. E-Diary Transmission

An e-diary will be considered transmitted if any data for the local reactions, systemic events, or use of antipyretic/pain medication are present for any day. If all data are missing for all items on the e-diary for all 7 days after vaccination, then the e-diary will be considered not transmitted. An e-diary will be considered completed if all expected data for all 7 days are available (ie, not missing). Otherwise, the e-diary will be considered incomplete. For any given day, an e-diary will be considered complete if all expected data are available.

3.5.3. Prior/Concomitant Vaccines and Concomitant Medications

The following concomitant medications and vaccinations will be recorded in the CRF:

- Ongoing medications, if taken, will be recorded and include start date, name of the medication, dose, unit, route, and frequency at Visit 1.
- All prior receipt of any COVID-19 vaccine.

- Date of licensed or investigational influenza vaccine within the 3 years prior to enrollment.
- Any vaccinations received from 28 days prior to Visit 1 until the last visit (Visit 3).
- Prohibited medications listed in Section 6.9.1 of the protocol, if taken, will be recorded and include start and stop dates, name of the medication, dose, unit, route, and frequency.
- Details of any concomitant medication taken to treat any prespecified local or systemic reactogenicity symptoms reported in the e-diary will be collected.

4. ANALYSIS SETS (POPULATIONS FOR ANALYSIS)

Analysis populations are defined for the statistical analysis of safety and immunogenicity results in Table 6. Data for all participants will be assessed to determine if participants meet the criteria for inclusion in each analysis population prior to unblinding and releasing the database, and classifications will be documented per standard operating procedures.

Table 6. Analysis Sets Description

| Participant Analysis Set | Description | | |
|--------------------------|---|--|--|
| Screened | All participants who sign the ICD. | | |
| Randomized | All participants who are assigned a randomization number in the IRT system. | | |
| Evaluable immunogenicity | All randomized participants who are eligible, receive the study intervention to which they were randomized, have at least 1 valid and determinate immunogenicity result from the blood sample collected within 27 to 42 days after vaccination, and have no major protocol violations. Participants will be grouped according to the vaccine as randomized in the analysis based on the evaluable immunogenicity population. | | |
| mITT immunogenicity | All randomized participants who receive the study intervention and have at least 1 valid and determinate assay result after vaccination. Participants will be grouped according to the vaccine as randomized in the analysis based on the mITT immunogenicity population. | | |
| Safety | All participants who receive at least 1 dose of the study intervention. Participants will be grouped according to the vaccine as administered in the analysis based on the safety population. | | |

For determination of the evaluable immunogenicity population(s), major protocol violations will be determined by the medical monitor. A major protocol violation is a protocol violation that, in the opinion of the sponsor clinician, would materially affect assessment of immunogenicity, eg, participant's receipt of a prohibited vaccine or medication that might affect immune response or a medication error with suspected decrease in potency of the vaccine. The sponsor clinician will identify those participants with a protocol violation prior to unblinding of the study.

5. GENERAL METHODOLOGY AND CONVENTIONS

Methodology for summary and statistical analyses of the data collected in this study is described here. The SAP may modify what is outlined in the protocol, where appropriate; however, any major modifications of the primary endpoint definitions or their analyses will also be reflected in a protocol amendment.

5.1. Hypotheses and Decision Rules

Two immunogenicity primary objectives and 4 immunogenicity secondary objectives have been defined for this study. The immunogenicity primary (Cohort 2) and secondary (Cohort 3) objectives involve a demonstration of NI of the immune responses measured 4 weeks after study intervention administration, and the immunogenicity secondary (Cohort 2) objective involves a demonstration of superiority of the immune responses measured 4 weeks after study intervention administration, as detailed below.

The immunogenicity primary objectives (Cohort 2) are to demonstrate NI of the immune response to CCI BNT162b2 (Omi XBB.1.5) at 4 weeks after vaccination compared to BNT162b2 (Omi XBB.1.5) administered concomitantly with QIV for all targeted strains (seasonal strains cCI recommended by WHO and the SARS-CoV-2 Omi XBB.1.5 strain).

The first immunogenicity secondary objective (Cohort 3) is to demonstrate NI of the HAI immune response for the matched seasonal influenza strains recommended by WHO (CCI) elicited by BNT162b2 (Omi XBB.1.5) at 4 weeks after vaccination compared to QIV alone.

The second immunogenicity secondary objective (Cohort 3) is to demonstrate NI of the SARS-CoV-2 immune response elicited by BNT162b2 (Omi XBB.1.5) at 4 weeks after vaccination compared to BNT162b2 (Omi XBB.1.5) alone.

The third immunogenicity secondary objective (Cohort 3) is to demonstrate NI of the HAI immune response for the matched seasonal influenza strains recommended by WHO elicited by CCI BNT162b2 (Omi XBB.1.5) at 4 weeks after vaccination compared to CCI Balone.

The fourth immunogenicity secondary objective (Cohort 2) is to demonstrate superiority of the HAI immune response to BNT162b2 (Omi XBB.1.5) at 4 weeks after vaccination compared to BNT162b2 (Omi XBB.1.5) administered concomitantly with QIV for all targeted strains CCI recommended by WHO.

For evaluation of the immunogenicity primary objectives (Cohort 2), 2 statistical hypotheses for each targeted strain will be defined as described below:

$$H_{01}: \ln(\mu_1) - \ln(\mu_2) \le \ln \frac{CCI}{I}$$
,

Where \ln CCI corresponds to a CCI margin for NI, and μ_1 and μ_2 are the GMTs from Arm C and Arm D, respectively, measured 4 weeks after vaccination.

$$H_{02}$$
: $\pi_1 - \pi_2 \le \frac{\text{CCI}}{2}$ %,

where π_1 and π_2 are the proportions of participants achieving seroconversion or seroresponse at 4 weeks after vaccination for Arm C and Arm D, respectively.

For evaluation of immunogenicity secondary objectives (Cohort 3), 1 statistical hypothesis for each target strain will be defined as described below:

$$H_{01}: \ln(\mu_1) - \ln(\mu_2) \le \ln(\Box),$$

where $\ln(\frac{\text{CCI}}{\text{CCI}})$ corresponds to a margin for NI and μ_1 and μ_2 are the geometric mean of titers in Arm E and the corresponding comparative vaccine (Arm F and Arm G and Arm H) groups, respectively, measured 4 weeks after vaccination.

For evaluation of the immunogenicity secondary objective (Cohort 2), 2 statistical hypotheses for each targeted seasonal strain (COMPAGE TRANSPORTED T

$$H_{01}: \ln(\mu_1) - \ln(\mu_2) \le \ln^{60}$$

where $\ln(1)$ corresponds to a margin for superiority and μ_1 and μ_2 are the geometric mean of titers from Arm C and Arm D, respectively, measured at 4 weeks after vaccination.

$$H_{02}: \pi_1 - \pi_2 \leq CCI_{0}$$

where π_1 and π_2 are the proportions of participants achieving seroconversion at 4 weeks after vaccination for Arm C and Arm D, respectively.

For each strain, NI based on GMR will be declared if the lower limit of the 2-sided 95% CI for the GMR is NI based on seroconversion or seroresponse (Cohort 2 only) will be declared if the lower limit of the 2-sided 95% CI for the difference in percentage of participants achieving seroconversion or seroresponse is greater than (Cohort 2 only) based on GMR will be declared if the lower limit of the 2 sided 95% CI for the GMR is superiority based on seroconversion (Cohort 2 only) will be declared if the lower limit of the 2-sided 95% CI for the difference in percentage of participants achieving seroconversion is COhort 2 only).

5.1.1. Multiplicity Adjustment

Hypothesis testing of the objectives for Cohort 2 (2 immunogenicity primary objectives and the fourth secondary objective) will be evaluated independently from that of Cohort 3 (3 immunogenicity secondary objectives) without applying any multiplicity adjustment.

Within Cohort 2, the immunogenicity primary objectives and the fourth secondary objective will be evaluated sequentially. The immunogenicity primary endpoints/estimands are considered coprimary. There are hypothesis tests (CCI) for XBB.1.5] for the immunogenicity primary NI objectives (CCI) for XBB.1.5] ws BNT162b2 [Omi XBB.1.5] administered concomitantly with QIV), with 2 statistical hypotheses for each of the targeted influenza and SARS-CoV-2 strains. Each hypothesis will be tested at a 1-sided alpha level of 0.025. The immunogenicity primary objectives will be achieved if NI is met for all statistical hypotheses. After the immunogenicity primary NI objectives (Cohort 2) are established, the statistical hypotheses for the fourth secondary objective (Cohort 2) will be tested sequentially in the following order of seasonal influenza strains:

CCI and the hypothesis will be tested first based on GMR and then based on the seroconversion rate for each strain. Therefore, the overall type I error rate within Cohort 2 is fully controlled.

Within Cohort 3, the 3 immunogenicity secondary objectives will be evaluated sequentially in the following order: comparing CCI /BNT162b2 (Omi XBB.1.5) with QIV for targeted influenza strains, CCI BNT162b2 (Omi XBB.1.5) with BNT162b2 (Omi XBB.1.5) for the SARS-CoV-2 Omi XBB.1.5 strain, and CCI /BNT162b2 (Omi XBB.1.5) with CCI for targeted influenza strains. There are hypothesis tests for the immunogenicity secondary NI objectives (CCI /BNT162b2 [Omi XBB.1.5] vs QIV for targeted influenza strains, 1 for CCI /BNT162b2 [Omi XBB.1.5] vs BNT162b2 [Omi XBB.1.5] for the SARS-CoV-2 Omi XBB.1.5 strain, and CCI /BNT162b2 [Omi XBB.1.5] vs CCI for targeted influenza strains). Each hypothesis will be tested at a 1-sided alpha level of 0.025. For objectives involving hypotheses for influenza strains, all hypotheses within the objective must be established before assessing the next objective in the sequence. Therefore, the overall type I error within Cohort 3 is fully controlled.

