where  $\ln(\frac{CCI}{CCI})$  corresponds to a margin for NI, and  $\mu_1$  and  $\mu_2$  are the GMTs from Arm C and Arm D, respectively, measured at 4 weeks after vaccination.

$$H_{02}$$
:  $\pi_1 - \pi_2 \le CC$  %,

where  $\pi_1$  and  $\pi_2$  are the proportions of participants achieving seroconversion or seroresponse at 4 weeks after vaccination for Arm C and Arm D, respectively.

For evaluation of immunogenicity secondary objectives (Cohort 3), 1 statistical hypothesis for each target strain will be defined as described below:

$$H_{01}: \ln(\mu_1) - \ln(\mu_2) \le \ln(\frac{CCI}{L})$$

where  $\ln(\text{CCI})$  corresponds to a  $\frac{\text{CCI}}{\text{margin for NI}}$  margin for NI, and  $\mu_1$  and  $\mu_2$  are the GMTs in Arm E and the corresponding comparative (Arm F and Arm G) and experimental (Arm H) vaccine groups, respectively, measured 4 weeks after vaccination.

For evaluation of the immunogenicity secondary objective (Cohort 2), 2 statistical hypotheses for each targeted seasonal strain ([CCI recommended by WHO) will be defined as described below:

$$H_{01}: \ln(\mu_1) - \ln(\mu_2) \le \ln(0)$$

where  $\ln(\Box)$  corresponds to a  $\square$  margin for superiority, and  $\mu_1$  and  $\mu_2$  are the GMTs from Arm C and Arm D, respectively, measured at 4 weeks after vaccination.

$$H_{02}$$
:  $\pi_1 - \pi_2 \le \%$ ,

where  $\pi_1$  and  $\pi_2$  are the proportions of participants achieving seroconversion at 4 weeks after vaccination for Arm C and Arm D, respectively.

For each strain, NI based on GMT will be declared if the lower limit of the 2-sided 95% CI for the GMR is CO NI based on seroconversion or seroresponse (Cohort 2 only) will be declared if the lower limit of the 2-sided 95% CI for the difference in percentages of participants achieving seroconversion or seroresponse is greater than CO (Section 1) superiority (Cohort 2 only) based on GMT will be declared if the lower limit of the 2 sided 95% CI for the GMR is CO (Superiority based on seroconversion (Cohort 2 only) will be declared if the lower limit of the 2-sided 95% CI for the difference in percentages of participants achieving seroconversion is CO

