6.1.2. Primary Immunogenicity Endpoints

6.1.2.1. Main Analysis

- Estimand(s) in Cohort 2:
 - GMR of HAI titers at 4 weeks after vaccination in participants who received BNT162b2 (Omi XBB.1.5) to those who received QIV administered concomitantly with BNT162b2 (Omi XBB.1.5).
 - The difference in percentage of participants with seroconversion to the seasonal strain at 4 weeks after vaccination between participants who received CCI BNT162b2 (Omi XBB.1.5) and those who received QIV administered concomitantly with BNT162b2 (Omi XBB.1.5).
 - GMR of SARS-CoV-2 (Omi XBB.1.5)—neutralizing titers at 4 weeks after vaccination in participants who received BNT162b2 (Omi XBB.1.5) to those who received BNT162b2 (Omi XBB.1.5) administered concomitantly with QIV.
 - The difference in percentage of participants with seroresponse to the SARS-CoV-2
 (Omi XBB.1.5) strain at 4 weeks after vaccination between participants who received
 BNT162b2 (Omi XBB.1.5) and those who received BNT162b2 (Omi XBB.1.5)
 administered concomitantly with QIV.
- Analysis set(s): Evaluable immunogenicity population and mITT immunogenicity population (as applicable) (Section 4).
- Analysis time point(s): 4 Weeks after vaccination.
- Statistical method(s): Analysis will be performed within each cohort independently. The unadjusted GMR and the associated 2-sided 95% CIs will be provided using methods described in Section 5.2.2.2. The difference in percentage of participants with seroconversion/seroresponse, and the associated 2-sided 95% CIs, will be calculated using the Miettinen and Nurminen method (Section 5.2.1). Seroconversion is defined as having an HAI titer <1:10 prior to vaccination and ≥1:40 at the postvaccination time point of interest, or an HAI titer of ≥1:10 prior to vaccination with a minimum 4-fold rise at the postvaccination time point of interest. Seroresponse is defined as achieving a ≥4-fold rise from baseline (before the study vaccination). If the baseline measurement is

below the LLOQ, the postvaccination measure of \geq 4 × LLOQ will be considered seroresponse. NI based on the GMR will be established if the lower bound of the 2-sided 95% CI for the GMR is greater than colored and NI based on the seroconversion/seroresponse rate difference will be established if the lower bound of the 2-sided 95% CI for the difference in percentage is greater than colored.

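### Does the Cohort 3 all-strains rule, worded as a gate to the next objective, leave type I error uncontrolled?

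*SAP*

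**What the plan says.** Cohort 3 compares the combination vaccine (Arm E) with QIV for the influenza strains, then with BNT162b2 for the SARS-CoV-2 strain, then with the standalone vaccine of Arm H for the influenza strains. SAP section 5.1.1 fixes that order, tests each hypothesis at 1-sided 0.025, and links the steps with this rule: "For objectives involving hypotheses for influenza strains, all hypotheses within the objective must be established before assessing the next objective in the sequence". Its conclusion is: "Therefore, the overall type I error within Cohort 3 is fully controlled".

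The criterion for a single hypothesis is in SAP section 5.1: "For each strain, NI based on GMR will be declared if the lower limit of the 2-sided 95% CI" meets the stated limit. Protocol section 9.1 has the same sentence: "For each strain, NI based on GMT will be declared if the lower limit of the 2-sided 95% CI". Neither is restricted to Cohort 2.

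For Cohort 2, section 5.1.1 says more. On the primary objectives: "The immunogenicity primary objectives will be achieved if NI is met for all statistical hypotheses". The superiority hypotheses "will be tested sequentially in the following order of seasonal influenza strains". The Cohort 3 paragraph of the SAP has no counterpart to either sentence. The Cohort 3 paragraph of protocol section 9.1.2 breaks off in the copy available here, so it cannot settle the matter.

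**The concern.** The all-strains condition is tied to moving on to the next objective. That leaves open what happens inside an objective when one strain misses. The third objective shows this most clearly: "The third immunogenicity secondary objective (Cohort 3) is to demonstrate NI of the HAI immune response for the matched seasonal influenza strains" against Arm H, with no later objective for the gate to protect. Set beside a sentence that declares noninferiority strain by strain, the text could be read as allowing the strains that passed to be claimed even when another failed.

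On that reading several hypotheses are each tested at 0.025 with no adjustment among them, and the claim of control would not follow. Two analysts could also make different formal claims from the same data. The contrast with Cohort 2, where a success rule and a strain order are both written out, makes the silence look like an omission.

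**Working it through.** **Inputs from the SAP.** 1-sided 0.025 per hypothesis and the fixed order of objectives (5.1.1); one GMR hypothesis per strain in Cohort 3 (5.1).

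**Assumptions.** The strain count is redacted, so 2, 3 and 4 are used. The correlation ρ between strain test statistics is not given, so 0 to 0.9 is used.

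**The stated level.** The lower limit of a 2-sided 95% interval corresponds to 1 − Φ(1.96) = 0.025, as stated. The SAP gives this per hypothesis. It gives no overall figure for Cohort 3.

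**Reading A: an influenza objective is achieved only if all its strains pass.** Take the earliest objective in the order that contains a false noninferiority hypothesis. Any false objective-level claim requires that objective to be achieved, because later ones are not assessed otherwise. Achieving it requires the false strain hypothesis to pass, which has probability at most 0.025. So the error over the whole sequence is at most 2.5%. A simulation of the sequence with three strains (1,000,000 runs) gave 2.5% with one strain at the margin and the others clearly noninferior, and 0.5% or less with all three at the margin (ρ from 0 to 0.7).

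**Reading B: each passing strain is claimed separately.** With all k strains of one objective at the margin and ρ = 0, the chance of at least one false claim is 1 − 0.975^k:

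- k = 2: 1 − 0.975² = 0.0494
- k = 3: 1 − 0.975³ = 0.0731
- k = 4: 1 − 0.975⁴ = 0.0963

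With equal correlation ρ it is 1 − E[Φ((1.96 − √ρ·X)/√(1 − ρ))^k], where X is standard normal:

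| ρ | B, 2 strains | B, 3 strains | B, 4 strains | A, 3 strains |
|---|---|---|---|---|
| 0 | 4.9% | 7.3% | 9.6% | <0.1% |
| 0.3 | 4.8% | 6.8% | 8.7% | <0.1% |
| 0.5 | 4.5% | 6.3% | 7.8% | 0.2% |
| 0.7 | 4.2% | 5.5% | 6.5% | 0.4% |
| 0.9 | 3.5% | 4.2% | 4.7% | 1.1% |

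The reading B figures for three strains also hold for the third objective once the first two have passed (simulated 7.3%, 6.8%, 6.3% and 5.5% at ρ = 0, 0.3, 0.5 and 0.7). With only one strain at the margin, reading B gives 2.5%, the same as reading A.

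**Which reading the text supports.**

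- The SAP infers control from the rule that all hypotheses within an objective must be established. That inference is valid under A and not under B.
- The per-strain sentence in 5.1 applies to Cohort 2 as well, where it coexists with an explicit all-strains rule. There it can only be the criterion for one hypothesis, and nothing gives it a different role in Cohort 3.
- The rule speaks of influenza objectives in the plural. Cohort 3 has two, the first and the last. A pure gate could bind only the first.
- Cohort 2 superiority has a strain order because it is tested strain by strain. The lack of an order in Cohort 3 suggests that separate strain claims were not planned.
- SAP section 6.2.1 states no noninferiority criterion, but it states no superiority criterion for Cohort 2 either, so its silence proves nothing. The criterion in section 6.1.2.1 ("NI based on the GMR will be established if the lower bound of the 2-sided" interval exceeds the limit) is itself written per hypothesis.

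**The case for a change.** The best case for a change is that a split across strains is realistic. Protocol section 2.2.3.2 reports that, in the sponsor's earlier Phase 3 modRNA influenza study, the secondary immunogenicity endpoints succeeded for the A strains and not for the B strains. If Cohort 3 splits in the same way, a reader would want to know in advance whether the passing strains carry formal claims, and a choice made after unblinding could look driven by the data.

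How often that would arise cannot be fixed from the documents, because the margin and the Table 7 entries are redacted. Assume 90% of Arms E and G evaluable (1080 and 540), three strains with correlation 0.3, and an SD of ln HAI between 0.9 and 1.3. The standard error factor is √(1/1080 + 1/540) = 0.0527. With all true GMRs at 1.0, some but not all strains pass in under 0.1% of trials at an assumed 1.5-fold margin, and in 1% to 23% at an assumed 1.25-fold margin. With one strain at 0.85 the figures are 0.1% to 6% and 75% to 85%. The range is set almost wholly by the assumed margin.

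What stands is that the success rule for the two influenza objectives is implied, not written, and that the gate by its literal wording does not reach the last objective. A split result is also plausible. It does not follow that error is uncontrolled: a split result under the all-strains reading means that the objective is not met and the strain results are descriptive.

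**Conclusion.** This is a gap in wording that analysts would fill sensibly. Requiring all strains for each influenza objective is the only one of the two readings under which the SAP's conclusion about Cohort 3 is true, and under it the error is at most 1-sided 2.5% whatever the margin, SD, strain count or correlation. The inflated figures (7.3% for three uncorrelated strains; 3.5% to 9.6% over two to four strains and ρ from 0 to 0.9) need two things together: single-strain results treated as confirmatory, which nothing in section 5.1.1 grants, and every strain of an objective sitting at the margin. With one strain there, no inflation occurs on either reading.

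These are secondary objectives. The GMRs and intervals are reported in both cases, and alpha, the order of objectives and the gate are untouched. A sentence spelling out the all-strains rule would do no harm, but it would alter no analysis. The conclusion rests on the SAP text, since the matching protocol paragraph is incomplete in this copy.
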